10.1.3. Reporting of Adverse Events

Guidelines for reporting of adverse events provided by the Stanford Institutional Review Board and the Food and Drug Administration (FDA) in the U.S. will be followed as summarized in Table 1 below.

Table 1. Guidelines for reporting adverse events

Institution	Type of Adverse Events	When to Report
Stanford IRB	Adverse event that Stanford PI determines: 
 • changes the study risks or benefits, 	
 • Within 10 working days of PI's awareness

	OR necessitates modification to the IRB-approved consent document(s) and/or the IRB-approved application/protocol	
FDA	
 Definitely, Probably or Possibly related AND BOTH Serious* AND Unexpected[‡] 	
 For fatal or life-threatening events, by telephone or fax within 7 calendar days of first awareness All other reportable events within 15 calendar days of first awareness

Serious Adverse Event (SAE) is any AE that results in any of the following outcomes:

- Death,
- Life-threatening adverse experience,
- Inpatient hospitalization or prolongation of existing hospitalization,
- Persistent or significant disability/incapacity,
- Congenital anomaly/birth defect, or cancer, or
- Any other experience that suggests a significant hazard, contraindication, side effect or precaution that **may require medical or surgical intervention** to prevent one of the outcomes listed above,
- Event occurring in a gene therapy study
- Event that changes the risk/benefit ratio of the study.

Unexpected Adverse Event An adverse event is defined as being unexpected if the event exceeds the nature, severity, or frequency described in the protocol, consent form and investigator brochure (when applicable). An unexpected AE also includes any AE that meets any of the following criteria:

- Results in subject withdrawal from study participation,
- Due to an overdose of study medication, or
- Due to a deviation from the study protocol

10 WITHDRAWAL OF SUBJECTS AND MANAGEMENT OF PROTOCOL VIOLATIONS

10.1 Withdrawal of subjects from the study

Participants will be followed until they reach 28 days post-randomization, with optional follow-up for up to 10 months. Study participants will be prematurely withdrawn from the study for: 1) inability to be located for >7 consecutive days, 2) withdrawal of informed consent, 3) inability to comply with the study schedule and procedures (e.g., missing 3 of the first 6 in-person visits), 4) at the discretion of the site investigator if the study is not in the best interest of the participant, 5) subject judged by the site investigator to be at significant risk of failing to comply with the study protocol as to cause them harm or seriously interfere with the validity of study results. If a subject is withdrawn for reasons # 1 or 2, we will be unable to perform any additional study procedures. If a subject is withdrawn for reasons # 3-5, plans to obtain appropriate follow-up tests outside of the study will be individualized for each subject depending on the health status of the subject at the time of withdrawal and the willingness of the participant and his or her parent/guardian to proceed with additional testing.

10.2 Protocol Violations

All protocol violations will be noted and reported to the Stanford Institutional Review Board within 5 days of the protocol violation report. The PI will develop a corrective action plan to present to the IRB for review and approval.

11 DATA SAFETY MONITORING

The proposed study will conform to rigorous standard monitoring procedures, standardized reporting of adverse events (Adverse Event Report Forms are completed by study coordinators and sent immediately to the investigators), and review of the study by a Data and Safety Monitoring Board (DSMB) at both an interim and final analysis. The PI has primary responsibility for the overall conduct of the study, including the safety of human subjects. The PI will ensure appropriate (1) conduct of the informed consent process (e.g. that informed consent is obtained before proceeding with study procedures); (2) enrollment of study subjects; (3) collection and analysis of data; (4) implementation of study procedures to ensure consistent monitoring of subjects for possible adverse events; (5) review of adverse events and reporting to the DSMB and the IRBs; and (6) maintenance of the privacy and confidentiality of study subjects. The PI maintains ultimate responsibility for the project and for the safety of study participants. The PI will be in contact with the research team on a regular basis to review the progress of the study and address any human subject issues that occur. These discussions may involve adverse event prevention measures, recruiting of appropriate study subjects, research staff training on protection of human subjects, as well as occurrence of adverse events, unexpected incidents, or protocol problems.

11.1. Data and Safety Monitoring Board

A DSMB will be established by the study team in cooperation with the sponsor to assess at intervals the progress of a clinical trial, safety data, and critical efficacy variables and recommend to the sponsor whether to continue, modify or terminate the trial. The DSMB will operate according to guidelines documented in a DSMB charter. Minutes will be taken to provide a written record of the DSMB meetings, including interim results; these will be available for review when the trial is complete. The DSMB will be a separate entity from the Institutional Review Board (IRB). The independence of the DSMB is intended to control the sharing of important comparative information and to protect the integrity of the clinical trial from adverse impact resulting from access to trial information. DSMB members will not participate in the study as investigators and will not have conflicts of interest regarding the study or the investigational product. The composition of the DSMB will include at minimum:

DSMB Chair, having experience and expertise in clinical trials

Scientist with expertise in viral infectious diseases.

Scientist with expertise in pharmacology

Biostatistician with expertise in clinical trials.

The DSMB will meet before the study, during an interim analysis, and at the conclusion of the trial to review progress of the clinical trial and safety data.

The DSMB will review the study for progress and safety. The PI will provide information that will allow the DSMB to review and assess the following:

- The research protocol, informed consent documents and plans for data safety and monitoring;
- Periodic assessments of data quality and timeliness, participant recruitment, accrual and retention, participant risk versus benefit, and other factors that can affect study outcome;
- Factors external to the study when relevant information, such as scientific or therapeutic developments, may have an impact on the safety of the participants or the ethics of the trial;
- Study performance to make recommendations and assist in the resolution of problems;
- The safety of the study participants;
- The safety and scientific progress of the trial;
- The continuation, termination or other modifications of the trial based on the observed beneficial or adverse effects of the treatment under study;
- The confidentiality of the data and the results of monitoring; and
- Any problems with study conduct, enrollment, sample size and/or data collection.

The first meeting of the DSMB will take place prior to the initiation of the study to discuss the protocol and the Data Safety Monitoring Plan. Meetings of the DSMB shall be held according to the plan outlined above. Meetings shall be closed to the public because discussions may address confidential patient data. Meetings may be convened as conference calls as well as in person. An emergency meeting of the Board may be called at any time should questions of patient safety arise. The DSMB may request the presence of study investigators at such meetings.

The study PI will distribute study information to the DSMB prior to a scheduled meeting. The DSMB may request additions and other modifications to this information on a one-time or continuing basis. This information will consist of two parts: (1) information on study progress such as accrual, baseline characteristics, and other general information on study status and (2) any confidential data on study outcomes, including safety data. A formal report from the DSMB should be supplied to the PI within 3 days of each meeting. Each report should conclude with a recommendation to continue or to terminate the study. This recommendation should be made by formal majority vote. A recommendation to terminate the study should be transmitted to the PI and IRBs as rapidly as possible, by immediate telephone and fax if sufficiently urgent. In the event of a split vote in favor of continuation, a minority report should be contained within the regular DSMB report. At the conclusion of the DSMB meeting for the interim safety review planned at 50% enrollment, the DSMB chair will convey the DSMB's recommendation to the study PI in order to minimize the amount of time enrollment is paused.

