8. STUDY TREATMENTS

8.1 Method of assigning subjects to treatment groups

Up to 120 eligible patients will be randomly assigned to Lambda or placebo in a 1:1 ratio to the treatment and control arms using a REDCAP-based computer-generated randomization scheme developed by the study data management provider. Randomization will be stratified by age ($>=50$ and <50 years old) and sex. The investigator or designee will complete a password-protected electronic spreadsheet containing the randomization allocation, along with the code used to generate the allocation along with the seed used in the random number generation, will be stored on secure servers at Stanford.

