8.2 Blinding

Administration of all study drugs will be single-blind (blinded to the study participant). All doses of study drugs will be prepackaged by the investigational pharmacist and administered by a study nurse not involved in data analysis. The study biostatisticians will be blinded to subject randomization, with the exception of an unblinded subgroup who will generate the randomization scheme and perform unblinded interim analyses. The subgroup will not discuss the unblinded data or interim results with the blinded biostatisticians and will save their materials on a server that is inaccessible to the blinded members. This study blind will be broken on completion of the clinical study and after the study database has been locked. During the study, the blind may be broken **only** in emergencies when knowledge of the patient's treatment group is necessary for further patient management. When possible, the Investigator should discuss the emergency with the data safety and monitoring board prior to unblinding.

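### Protocol 11.1 makes the PI the sender of confidential outcome data to the DSMB, which can expose the PI to comparative interim results with about half the patients still to enrol

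*Protocol*

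**What the plan says.** **Who supplies the DSMB.** Protocol 11.1 says that "The study PI will distribute study information to the DSMB prior to a scheduled meeting". It divides the material in two: a progress part (accrual, baseline characteristics, general status) and a second part consisting of "any confidential data on study outcomes, including safety data". A list earlier in the same section sets out what the PI's information must allow the board to judge, including whether to continue, stop or modify the trial "based on the observed beneficial or adverse effects of the treatment under study". Protocol 11.2 and SAP section 5 describe the interim review but name no sender.

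**What is meant to be protected.** Protocol 11.1 also says: "The independence of the DSMB is intended to control the sharing of important comparative information". It makes the board's minutes, which include interim results, available for review only when the trial is complete. Protocol 8.2 blinds the participants and the study biostatisticians, apart from "an unblinded subgroup who will generate the randomization scheme and perform unblinded interim analyses". That subgroup may not share unblinded data or interim results with the blinded biostatisticians, and it stores its files where they cannot reach them.

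**Who holds the allocation.** Protocol 8.1 credits the randomization scheme to the data management provider. It then reads "The investigator or designee will complete a password-protected electronic spreadsheet containing the randomization allocation, along with the code used to generate the allocation", in a sentence that goes on to mention the seed and ends with a second main verb about storage on secure servers. SAP 1.5 does not say who holds the list.

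**The concern.** The usual arrangement is that a statistician outside the trial team prepares the comparative report and passes it straight to the board. The protocol already has suitable people in the unblinded subgroup, but 11.1 names the PI as the sender. Under Protocol section 11 the same person is responsible for enrolling subjects and for collecting and analysing the data.

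Four things would be open to influence if the PI came to know how the arms compare at the interim:

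- **Recruitment.** Knowledge of an emerging benefit or harm can change who is approached and enrolled after the pause.
- **Withdrawal.** The site investigator may withdraw a participant when the study is not in that person's best interest (Protocol 10.1 on withdrawal). A withdrawn patient without the endpoint is censored (SAP 1.2 and section 3) and, not having completed follow-up, leaves the per-protocol set (Protocol 12.1).
- **Adverse event forms.** A severe event that is neither serious nor unexpected gets a report form only if it is judged possibly, probably or definitely related to study drug (Protocol 10.1.2).
- **Re-sizing.** Protocol 12.6 and SAP section 6 allow the sample size to change, or the trial to stop for futility, if the standard of care changes before enrolment is 90% complete. They undertake not to use outcome data in doing so. That undertaking is harder to defend if the PI has handled the interim outcome package.

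**Working it through.** There is no stated figure to reproduce. The check is a comparison of the texts, plus one line of arithmetic on exposure.

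1. **Is the PI the named sender of outcome data?** Yes. Protocol 11.1 says so for both parts of the package, and neither document gives a different route.
2. **Must the interim material be comparative?** In large part. Protocol 11.2 and SAP section 5 have the board review efficacy on all randomised participants, using the final-analysis methods in the ITT population, with a stopping threshold of p<0.00001. The final analysis is a Cox model comparing the arms (Protocol 12.3), and a p-value from that model cannot come from pooled data. The list in 11.1 points the same way, since the PI's information must support a decision on observed treatment effects.
3. **Does 11.1 say that the PI's package is by arm?** No. Steps 1 and 2 together make that the natural reading, but it remains an inference.
4. **Does this conflict with the plan's own safeguards?** It conflicts with the reason given in 11.1 for an independent board, and with holding back the minutes until the trial is complete. It also sits badly with 8.2, where the blind is broken after database lock and otherwise only in emergencies, if possible after the investigator has consulted the board. That rule implies that the investigator is not expected to hold treatment-group information routinely.
5. **Does it breach the explicit separation in 8.2?** Not in terms. That separation is between two groups of biostatisticians. The PI is not mentioned, and no section states whether the PI is blinded.
6. **How many patients are exposed?** Enrolment pauses once 50% have been treated. Of 120 planned, 0.50 × 120 = 60 are in before the review, and 120 − 60 = 60 are randomised after it.
7. **How much would the interim show?** The board sees 24-hour safety data on all enrolled patients. Day-5 blood counts are expected in about 25%, and the base is not stated: 0.25 × 60 = 15 patients, or 0.25 × 120 = 30. The primary endpoint needs two consecutive negative oropharyngeal tests (Protocol 5.1), so efficacy data would be thin, while early safety data would be fairly complete.
8. **The allocation file.** Read literally, 8.1 has the investigator or a designee completing the spreadsheet that holds the allocation and its generating code. The sentence has two competing predicates, so words have probably been lost or two sentences merged. Separately, 8.1 attributes the scheme to the data management provider and 8.2 to the unblinded subgroup.

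**The case against.** The strongest reply is that this is loose wording about logistics. Distributing a package is not the same as reading it. The subgroup in 8.2 still performs the unblinded interim analysis, and nothing in 11.1 reverses that. Protocol 11.1 also says that the board works under a charter, and the charter may provide for a sealed closed report. These points stand as limits: they make exposure possible rather than certain. They do not remove the problem, because the protocol names the PI and does not defer to the charter on this matter.

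The second reply is that the harms are bounded and partly have another cause. This also has force. Only the participant is blinded on administration and the placebo syringe does not match (Protocol 8.3.2), so bias from knowing an individual patient's arm would survive any change of report route. All adverse events are captured whatever their severity, on the same case record form in both arms, and serious or unexpected events always get a report form. The primary analysis is ITT, and the endpoint is a laboratory PCR result. What the route adds is knowledge of the aggregate comparison, which participant-only blinding does not by itself give the PI.

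Two stronger readings are tempting and should be resisted:

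- A reader might infer that 11.1 defeats the separation set up in 8.2. The text does not go that far, because that separation is between biostatisticians and does not cover the PI.
- A reader might infer from 8.1 that allocation concealment is open for all 120 patients. That would rest on one ungrammatical sentence, in a section that also describes a computer-generated REDCap scheme developed by a data management provider. The sentence needs repair but does not establish that the investigator holds the list.

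**Conclusion.** The point holds as a gap in the protection of interim results and should be corrected. By Protocol 11.1 the PI sends the confidential outcome and safety data; by 11.2 the interim review includes a comparative ITT efficacy analysis. The route as written can therefore expose the PI to comparative results before about 60 of 120 patients are enrolled. This is at odds with the stated purpose of the board's independence and with the restricted handling of unblinded analyses in 8.2.

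The conclusion rests on two assumptions: that the material the PI sends includes the analysis the board is to review, and that the charter does not set a different route. The documents settle neither. The size of any bias cannot be calculated from them. It is probably limited for the PCR primary endpoint under ITT, and larger for recruitment after the pause and for judgements about relatedness. The defect in 8.1 is secondary: a drafting repair and an unresolved question of who generates and holds the scheme.

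**What to change.** **Main change, Protocol 11.1 (mirrored in SAP section 5).** State that the unblinded statistical subgroup of section 8.2 prepares the closed report, with outcomes and safety by arm, and sends it directly to the DSMB. State that the PI supplies only the open part (accrual, pooled baseline and progress data) and does not receive comparative interim results. If the charter already provides for this, bring 11.1 into line with it and cite it.

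**Secondary change, Protocol 8.1.** Rewrite the broken sentence so that it cannot be read as giving the investigator the allocation, code and seed. Say once who generates the scheme and who holds it, reconciling the data management provider in 8.1 with the unblinded subgroup in 8.2. The code and seed should not pass to any further party in the process.

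It would also help to state in 8.2 whether the PI is blinded, and to reconcile the open-label description in Protocol 4.1 with the single-blind description elsewhere.

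**Cost.** A few sentences in the protocol and one in the SAP. The unblinded subgroup already exists and already runs the interim analysis, so no new staff are needed and neither the design nor the sample size changes.

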11.2. Interim analysis

An interim analysis for safety and overwhelming efficacy will be performed once 50% of patients have 24 hours of follow-up complete. Enrollment will pause once 50% of patients have received treatment and will remain paused until the DSMB makes their recommendation after their safety review. The DSMB will meet one or two days after enrollment is paused to review the safety data collected within the first 24 hours of follow-up on all enrolled patients. We additionally

expect blood count labs collected at day 5 to be available in approximately 25% of patients at the time of the DSMB review.

The DSMB will also review the efficacy data on all randomized participants at this meeting. The interim efficacy analysis will use the same methods as are planned for the final analysis using the ITT analysis. Based on the results of the interim analysis, the DSMB will either recommend to the sponsor to terminate the study for overwhelming efficacy ($p<0.00001$ at the interim analysis), terminate the study for safety concerns, modify the study, or continue the study as planned. No formal stopping rules for futility are planned.

12 STATISTICAL METHODS AND CONSIDERATIONS

12.1 Analysis population

We will evaluate the intention-to-treat (ITT) population. The intent-to-treat (ITT) population will include all randomized patients. Patients will be analyzed according to their assigned treatment arm. All efficacy analyses will be completed in the ITT population. The per-protocol (PP) population will include all randomized patients who completed follow-up and adhered to study procedures. All efficacy analyses will be also be completed in the PP population as supportive evidence for the primary efficacy analysis. The safety population will include all patients who receive study treatment. Patients will be analyzed according to actual treatment received. All safety analyses will be completed in the safety population.

12.2 Descriptive analyses

Descriptive statistics (proportions for categorical variables, means, medians, standard deviations and interquartile ranges for continuous variables) will be reported for all key patient variables, including baseline and demographic characteristics, use of medications, compliance, and study completion status. Data that are missing on key patient characteristics and the outcome will be fully described, including any patterns of missingness (i.e., any relationships between missingness of a variable and patient characteristics).

A CONSORT diagram displaying the number of patients screened, eligible, and consented along with reasons for ineligibility will be provided. Graphical tools such as histograms, boxplots, and scatterplots will be created to assess quality of data and to display patterns over time.

12.3 Analysis of primary endpoint

Time until shedding cessation will be compared between the two treatment arms using a two-sided Cox proportional hazards model adjusted for age and sex. The test will be performed at the alpha = 0.05 level of significance. The hazard ratio for shedding cessation will be estimated, along with its 95% confidence interval, from a Cox proportional hazards model. If the proportional hazards assumption is not met, we will consider an extended Cox model that relaxes the proportional hazards assumption.

The distribution of shedding cessation will be estimated using the Kaplan-Meier method, and Kaplan-Meier curves will be presented for each treatment arm. Time to shedding cessation at the end of the study period along with 95% confidence intervals will be presented for each treatment arm.

In a subgroup analyses, the time until shedding cessation analyses will be performed separately in the symptomatic and asymptomatic participants.

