6.2 Inclusion Criteria

Patients must fulfill all of the following inclusion criteria to be eligible for the study:

1. Age \geq 18 years and \leq 75 years at the time of the assessment
2. Able and willing to understand the study, adhere to all study procedures, and provide written informed consent
3. Diagnosis of COVID-19 disease:
 - a. If symptomatic, presence of mild to moderate symptoms without signs of respiratory distress, with FDA-cleared molecular diagnostic assay positive for SARS-CoV-2 within 72 hours from swab to the time of commencing informed consent:
 - b. If asymptomatic, initial diagnosis of SARS-CoV-2 infection with positive FDA-cleared molecular diagnostic assay obtained no more than 72 hours from initial swab to the time of commencing informed consent

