12.6 Sample size and randomization

For the primary comparison, the following will be tested:

- Null hypothesis: time to cessation of oral shedding is equal in control and treatment;
- Alternative hypothesis: time to cessation of oral shedding differs between control and treatment.

Hypothesis tests will be two sided and conducted at an overall alpha = 0.05 level of significance.

We assume that the mean duration of virologic shedding in individuals receiving standard of care is 14 days, with a standard deviation of 4 days¹.

Assuming 1:1 randomization and the use of a two-sided log rank test at the alpha=0.04999 level of significance for the final analysis, 79 events will provide 80% power to detect a hazard ratio of 2.03. This leaves alpha=0.00001 to check for overwhelming efficacy after 50% of participants have completed 24 hours of follow-up. Assuming the control and treatment arm median cessation of shedding is 14 and 7 days, respectively, a two-month accrual period, a two-week follow-up period after randomization of the last patient, and a drop out of 10% in the control arm, it is estimated that the total sample size required to achieve 79 events is 120 (60 patients in each arm).

As described in section 6.6 above, we provide the following power calculations showing how potential study alterations due to slow enrolment would impact the study's operating characteristics. If fewer than 10 patients have been enrolled within the first two weeks, a potential solution to increase enrollment is to change the randomization ratio to be 2:1 on treatment:control, which would reduce the chance of being randomized to placebo to 33%. Under the assumptions described above, the change in the randomization ratio will not require a larger sample size.

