## 1.5 Randomization scheme

Patients will be randomized in a 1:1 ratio to the treatment and control arms. Randomization will be stratified by age ( $\geq 50$  and  $< 50$  years old) and sex.

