## 2.7 Effect modification, subgroup, and sensitivity analyses

A subgroup analysis will be performed for the primary endpoint using only patients who present with symptoms at baseline.

A statistical interaction term between treatment arm and the following baseline characteristics will be added to the Cox proportional hazards model to test for effect modification.

- 1) CT value < 30 from the baseline OP swab,
- 2) presence of antibodies as defined by presence of IgG antibodies to SARS-CoV-2 Spike Receptor Binding Domain (RBD) at baseline, as measured by ELISA. Samples are considered seropositive against RBD if their absorbance value was greater than the mean of plus four standard deviation (SD) of all negative controls (n=130),
- 3) number of risk factors or predictors for severe disease present at baseline (temp 99.5+, cough, or shortness of breath present at randomization [symptoms count as a single risk factor], age  $\geq$  60, male sex, Black race, Hispanic ethnicity, BMI  $\geq$  30, and lab values of baseline lymphocyte counts <1000 and baseline ALT  $\geq$  94),
- 4) age  $\geq$  50,
- 5) sex

A Wald test performed at the alpha = 0.05 level of significance will be used to test whether the effect modification is statistically significant. The sensitivity and effect modification analyses will be performed in other key endpoints as well.

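### Protocol and SAP disagree on the symptom-status subgroup, and neither tests whether the treatment effect differs by symptom status

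*Protocol*

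**What the plan says.** Protocol 12.3, after describing the Cox model and Kaplan-Meier curves for the primary endpoint, adds one sentence on subgroups: "the time until shedding cessation analyses will be performed separately in the symptomatic and asymptomatic participants". It plans no interaction term for this or any other factor.

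SAP 2.7 reads differently: "A subgroup analysis will be performed for the primary endpoint using only patients who present with symptoms at baseline". No asymptomatic fit is mentioned.

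The same SAP section does have a method for effect modification: "A statistical interaction term between treatment arm and the following baseline characteristics will be added to the Cox proportional hazards model". The list has five entries: baseline CT below 30, baseline antibodies, number of risk factors, age 50 or over, and sex. On testing it says: "A Wald test performed at the alpha = 0.05 level of significance will be used to test whether the effect modification is statistically significant". Symptom status is not listed. The nearest item is the risk-factor count, where raised temperature, cough or shortness of breath together add one point ("symptoms count as a single risk factor"). That is not the same as symptomatic versus asymptomatic.

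Symptom status is an entry category of its own. Protocol 6.2 admits symptomatic patients under 3a and asymptomatic patients under 3b ("If asymptomatic, initial diagnosis of SARS-CoV-2 infection with positive FDA-cleared molecular diagnostic assay"). It is not a randomisation stratum; the strata are age and sex (SAP 1.5). Neither document gives an expected asymptomatic share.

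**The concern.** Two things are open. First, the documents do not agree on whether an asymptomatic analysis will be done. Second, whichever is followed, whether Lambda works differently in the two groups is not tested. A pair of within-group tests does not answer that question. The larger group has more events and is more likely to reach significance, so a difference in p-values can appear when the effects are identical. A symptomatic-only fit avoids the contrast but leaves the reader with a one-sided picture.

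At stake is the reading of an exploratory subgroup, the only one that both documents name for the primary endpoint. SAP 2.7 also carries its sensitivity and effect-modification analyses over to other key endpoints, so the gap would carry over too.

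**Working it through.** **Inputs**
- 79 events, 80% power, HR 2.03, two-sided alpha 0.04999, 1:1 allocation: Protocol 12.6 and SAP 4.2.
- HR 1.6 as a smaller effect: one of the reduced values considered in Protocol 12.6 and SAP 6.
- Subgroup tests at two-sided 0.05: the SAP 2.2 default.
- Asymptomatic share 10%, 20% or 30%: **assumed**.
- Events split in proportion to the share, the two groups are independent, and the true HR is the same in both: **assumed**.

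**Step 1. The plan's own event count.** Schoenfeld: 4 × (1.960 + 0.842)² / (ln 2.03)² = 62.6, so 63 events. Freedman: (1.960 + 0.842)² × (3.03/1.03)² = 67.9, so 68. Neither gives 79. By Schoenfeld, 79 events give Φ(0.708 × √79 / 2 − 1.960) = Φ(1.187) = 88% power. I keep 79 because it is the stated figure, and check in step 4 that the choice matters little.

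**Step 2. Separate fits under a uniform effect.** With d events in a group, power = Φ(ln(HR) × √d / 2 − 1.960). The chance of the misleading pattern is power(symptomatic) × [1 − power(asymptomatic)]. Example, HR 2.03 and a 20% share:
- Symptomatic: 63.2 events, Φ(2.814 − 1.960) = 0.804.
- Asymptomatic: 15.8 events, Φ(1.407 − 1.960) = 0.290.
- Product: 0.804 × 0.710 = 0.57.

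| True HR in both | Asymptomatic share | Events (sympt. / asympt.) | Power sympt. | Power asympt. | Sympt. significant, asympt. not | Reverse pattern |
|---|---|---|---|---|---|---|
| 2.03 | 10% | 71.1 / 7.9 | 0.847 | 0.167 | 0.706 | 0.026 |
| 2.03 | 20% | 63.2 / 15.8 | 0.804 | 0.290 | 0.570 | 0.057 |
| 2.03 | 30% | 55.3 / 23.7 | 0.749 | 0.407 | 0.445 | 0.102 |
| 1.6 | 10% | 71.1 / 7.9 | 0.509 | 0.097 | 0.459 | 0.048 |
| 1.6 | 20% | 63.2 / 15.8 | 0.463 | 0.152 | 0.393 | 0.082 |
| 1.6 | 30% | 55.3 / 23.7 | 0.416 | 0.207 | 0.330 | 0.121 |

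**Step 3. The interaction test instead.** The standard error of the difference in log HRs is √(4/d₁ + 4/d₂) = 0.750, 0.563 and 0.491 at shares of 10%, 20% and 30%.
- If the effects are equal, the test signals a difference in 5% of trials by design.
- If the HR is 2.03 in symptomatic and 1.0 in asymptomatic patients, power = Φ(0.708/SE − 1.960), or about 16%, 24% and 30%.
- For 80% power the ratio of HRs would have to be exp(2.802 × SE), or about 8.2, 4.8 and 4.0.

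**Step 4. Robustness.** With 63 events in place of 79, the HR 2.03 figures in step 2 become 65%, 54% and 43%. Simulated Cox fits (120 patients, HR 2.03 in both groups, about 400 runs per setting) gave 77% to 80%, 57% to 59% and 44% to 48% at the three shares. The interaction test's false-signal rate in simulation was 2% to 6.5%. The formula is roughest at the 10% share, where the asymptomatic fit has about eight events.

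**The case against.** The SAP is the more detailed analysis document. Under it, no asymptomatic estimate or p-value is produced, so the contrast in step 2 has no second half. Its symptomatic-only fit could be meant as a restricted-population sensitivity check, since the section covers sensitivity analyses and uses interaction terms where effect modification is the aim. This stands: the percentages apply to the protocol sentence only.

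A reader might infer that the plan sets out to conclude that Lambda works only in symptomatic patients. The documents do not support that. Neither says that subgroup p-values will be compared or that a subgroup result will support a claim of differential effect. Protocol 12.3 also calls for hazard ratios with confidence intervals and for Kaplan-Meier curves, which would show how imprecise a small group is. The misreading is a foreseeable risk, not something the plan states.

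A reader might also infer that the SAP has no proper effect-modification method. It has one, for five factors; one factor is missing from the list.

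Finally, an interaction test with 16% to 30% power settles little, and a null result could be misread as proof of equal effects. That is correct. It argues for reporting the estimate and its interval, not for comparing two p-values, since the asymptomatic fit is itself weak (17% to 41% power at HR 2.03).

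**Conclusion.** The point holds in limited form. The mismatch between Protocol 12.3 and SAP 2.7 is plain on the text, and symptom status is absent from the SAP's interaction list. If the protocol's separate fits are run, a uniform effect produces the misleading pattern in roughly 45% to 71% of trials at HR 2.03 and 33% to 46% at HR 1.6, against 5% false signals from an interaction test. If the SAP alone is followed, the rate is nil, and the cost is a missing asymptomatic estimate.

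The sizes rest on the assumed 10% to 30% share, events proportional to share, and a normal approximation. They are not sensitive to whether 79 or 63 events are used. The matter is exploratory and minor, and has no bearing on the validity of the primary comparison.

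**What to change.** 1. Reconcile Protocol 12.3 and SAP 2.7 so that both describe the same symptom-status analysis.
2. Add baseline symptom status (yes/no) as a sixth factor in the SAP 2.7 interaction list.
3. From that one model, report the hazard ratio and 95% CI in each group, and the ratio of hazard ratios with its 95% CI. Give no within-group p-values.
4. Label the analysis exploratory, and state that a non-significant interaction does not show equal effects.

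The cost is a few lines of text and one more low-power exploratory test. If the tests were independent and unadjusted, going from five to six would raise the chance of at least one false signal from 1 − 0.95⁵ = 23% to 1 − 0.95⁶ = 26%. No new data are needed, because both documents already rely on symptom status at baseline.
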